| Study Identification | BZ371CLI003 |
| Study description | Single dose, single center, non-blinded |
| Dosage and Administration | BZ371A, at a concentration of 5 mg/mL, applied to the genital area (entire penis including glans, clitoris, labia majora and minora) in a volume of 1.5 mL. The genital area should be washed with water and mild soap beforehand, followed by drying. The product should be applied using gloves. |
| Objectives | 
 • Determine safety and tolerability of BZ371A when topically Applied to genitália of healthy men and women • Evaluate systemic presence of BZ371A, or its fragments, through a pharmacokinetics study using blood, when BZ371A is topically applied. |
| Outcomes | 
 • Safety 
 ○ Adverse Events Report ○ Physical Exam in the genital region ○ Vital signs, including heart rate and systolic blood pressure ○ Electrocardiogram (ECG) ○ Laboratorial Exam, including (i) complete blood count, including platelets; (ii) coagulation profile, including prothrombin time (PT) and activated partial thromboplastin time (aPTT); (iii) biochemistry, including glucose, sodium, potassium, urea, creatinine, chloride, total calcium, phosphorus, total proteins and fractions (albumin and globulin), aspartate aminotransferase (AST), alanine aminotransferase (ALT), alkaline phosphatase, gamma-glutamyl transferase (GGT), total cholesterol, HDL cholesterol, triglycerides, pH; (iv) urinalysis for abnormal elements and sediment (AES). • PK analysis 
 ○ Detection of BZ371A and its fragments in the blood at the following collection times: pre-dose, 15, 30, 60, 180, and 360 minutes. ○ If detected, determine the pharmacokinetic parameters: maximum concentration (Cmax), half-life (t_{1/2}), area under the curve (AUC), clearance (CL), distribution volume (Vd). |

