BZ371A increases the expression of inducible NOS (iNOS), an enzyme that produces NO and is present in all cells, including the smooth muscle cells of the corpus cavernosum, which need to be distended to achieve an erection. It also increases the action of neuronal NOS (nNOS), present in the nerve endings of the penis. By acting independently of the autonomic nerves and the integrity of the pelvic vessels, BZ371A can act in prostatectomized patients, increasing local NO production and preventing penile mass loss. This combined dual action allows for a rapid onset and long-lasting effect necessary for the treatment of prostatectomized patients.

In addition, by increasing NO, BZ371A will present a synergistic effect with PDE5i, allowing this class of drugs to perform their action of maintaining blood flow, once stimulated by NO.

According to preclinical studies, BZ371A is a gel, considered safe, practical, and tolerable for topical use. In these studies, when applied topically, BZ371A did not show systemic bioavailability and, therefore, did not cause typical side effects of systemic vasodilators, such as arterial hypotension.

The aim of this study is to confirm whether BZ371A topically applied, is safe, tolerable, and does not show systemic bioavailability in humans.

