2.2 Endpoints

For safety and tolerability analysis of BZ371A, the following outcomes were considered:

- Report of adverse events (AE);
- Local physical examination of the genital area;
- Vital signs, including systemic blood pressure (BP) and heart rate (HR);
- Electrocardiogram (ECG);
- Laboratory tests, including (i) complete blood count, including platelets; (ii) coagulation profile, including prothrombin time (PT) and activated partial thromboplastin time (aPTT); (iii) biochemistry, including glucose, sodium, potassium, urea, creatinine, chloride, total calcium, phosphorus, total protein and fraction (albumin and globulin), aspartate aminotransferase (AST), alanine aminotransferase (ALT), alkaline phosphatase, gamma-glutamyl transferase (GGT), total cholesterol, HDL cholesterol, triglycerides, and pH; (iv) urinalysis for abnormal elements and sediments (EAS).

For pharmacokinetics analysis of BZ371A, the following outcomes will be considered:

- Detection of BZ371A and its fragments in the blood at the following timepoints: pre-dose, 15, 30, 60, 180, and 360 minutes;
- If detected, determination of the pharmacokinetic parameters: maximum concentration (Cmax), half-life (t_{1/2}), area under the curve (AUC), clearance (CL), volume of distribution (Vd).

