3. STUDY PLAN

3.1 General study design

Open-label study, conducted at a single center, with the aim of being the first human trial with the new BZ371A formulation in order to guide future clinical studies such as to understand safety, tolerability, and systemic bioavailability of the peptide topically applied.

The study will comprise only one group, consisting of 6 men and 6 women.

The formulation will be administered in a single dose, topically, followed by medical and laboratory analyses for safety assessment, and blood collections for pharmacokinetic analysis.

The concentration of BZ371A and its fragments in the blood will be measured by an appropriate analytical method, developed for this purpose and previously validated. The collected blood will be

analyzed by the company *Unidade Integrada de Farmacologia e Gastroenterologia* (UNIFAG), the same company that validated the analytical method, and will not be stored or used for any other purpose.

The visits and procedures are illustrated in the table below:

CHART 1. VISITS AND BZ371CLI003 STUDY PROCEDURES

| Visit | V-1 | V0 | V1 |
|--|-----------|-----------------------|-----------------|
| Day | D-1 | D0 | D7 |
| Interval | -7 a 0 | 0 | +2 a -2 |
| Visit Name | Screening | PK | Safety revision |
| ICF | X | | |
| Demographic data | X | | |
| Medical history | X | X | |
| Physical exam | X | | X |
| Genitalia exam | X | X / X ^(*) | X |
| Anthropometric data | X | | |
| Vital Signs | X | X / X ^(**) | X |
| Concomitant medication | X | X | X |
| Blood collection for laboratory analysis | X | X ^(*) | |
| Urine collection | X | X ^(*) | |
| Electrocardiogram | X | X ^(*) | X |
| Eligibility | X | X | |
| Blood sample collection for PK | | X | |
| BZ371A application | | X | |
| AE collection | | X | X |
| Next visit scheduling | X | X | |
| Study dismissal | | | X |

^{*}: after 360 minutes after IP application

^{**}: after IP application at 30, 60, 180 and 360

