5.3 Pharmacokinetics analysis procedure

5.3.1 *Blood sample collection procedure*

The collection of blood samples will be done through a heparinized catheter inserted into the superficial vein of the volunteer's forearm. After each blood collection, the catheter will be washed with 1 mL of sodium heparin solution (5000 IU/mL in 0.90% sterile NaCl). Samples will be collected at the following times: immediately before the application of PSI, and 15, 30, 60, 180, and 360 minutes after the application of PSI.

In total, 6 samples of approximately 4.9 mL (5 mL tube) of blood will be collected from each participant for the BZ371A dosage. Thus, approximately 29.40 mL of blood will be used for the pharmacokinetic study. In addition, adding to the 40 mL for laboratory tests before and after the application of PSI, a total of approximately 69.40 mL of blood will be collected during the study period for each participant.

The absolute real time of each blood sample collection should be recorded in the Clinical Record Forms (CRF) using a 24-hour clock. The absolute real time of the IP application should also be recorded,

so that the actual time interval between the application of IP and the respective collections can be computed. Any loss of sample collection should also be recorded. The collected samples should allow for the unequivocal identification of the study, research subject (identification code), collection period, and time.

In this study, yellow tubes with clot activator and gel separator will be used for blood sample collection. These two components cause the blood to clot more quickly, and after clotting, the gel performs the physical separation between the cellular and liquid (serum) portions. After collection, the samples should be kept in an ice bath at $4^{\circ}\text{C} \pm 2^{\circ}\text{C}$ from collection until centrifugation.

5.3.2 *Blood sample processing and storage*

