The blood samples will be centrifuged at approximately 3,000 rpm for 10 minutes at 4°C ($\pm 2^{\circ}\text{C}$). Immediately after centrifugation, a minimum of 1.2 mL of serum from each sample will be collected and aliquoted into 3 transparent Eppendorf LoBind tubes with a maximum capacity of 1.5 mL. The minimum volume of serum collected will be 1.2 mL and will be divided equally among the 3 tubes (e.g., if exactly 1.2 mL of serum is collected, each Eppendorf LoBind tube will have approximately 400 μL of volume). The remaining serum will be transferred to another cryogenic tube as a reserve sample.

Lo Bind Eppendorf tubes will be stored in polypropylene boxes labeled with the study name, study code, period, and subject number. These boxes will be stored at a temperature $< -70^{\circ}\text{C} \pm 5^{\circ}\text{C}$ in a specific freezer for the storage of biological samples, at the research center.

The period between sample collection, centrifugation, and storage in the freezer should not exceed 30 minutes.

5.3.3 *Blood sample transportation and analysis*

The transportation of samples from the storage unit to the analytical unit will be carried out in thermal boxes containing dry ice and a digital thermometer where the maximum and minimum temperatures reached are recorded.

The company *Unidade de Integração Farmacologia e Gastroenterologia* (UNIFAG) is the analytical company that will quantify BZ371A and its fragments in the samples.

If the peptide or its fragments are detected, the following pharmacokinetic parameters must be determined: maximum concentration (C_{max}), half-life (t_{1/2}), area under the curve (AUC), clearance (CL), volume of distribution (V_d).

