9. STATISTICAL ANALYSIS PLAN

The statistical analyses will aim to describe the pharmacokinetic parameters. Adverse events (AEs) will be analyzed qualitatively. Therefore, every detected adverse event will be described in the results, characterized by: (i) identification, if possible, as a medical entity (sign, symptom, or disease); (ii) intensity (mild, moderate, or severe); (iii) severity, whether it is a serious adverse event (resulting in death, abortion, immediate risk of death, hospitalization or prolongation of hospitalization, or disability); (iv)

duration; (v) resolution (complete, partial, or unresolved); (vi) mode of resolution (spontaneous or requiring medicinal treatment); and (vii) causality with the investigational product (IP).

Participants in whom the IP has been administered will be included in the analysis.

A sample size of 12 participants is considered adequate for a pharmacokinetic curve.

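### If analyte is detected, the plan requires CL and Vd, which one topical dose with unknown bioavailability cannot give; the female application lists also differ

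*Combined protocol and SAP*

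**What the plan says.** Three places set the pharmacokinetic parameters. The synopsis (Outcomes) has "If detected, determine the pharmacokinetic parameters", Section 2.2 repeats this as an endpoint, and Section 5.3.3 makes it an obligation: "If the peptide or its fragments are detected, the following pharmacokinetic parameters must be determined". All three list Cmax, t1/2, AUC, CL and Vd. None writes these as apparent values or divides by F.

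On design, Section 3.1 says "The formulation will be administered in a single dose, topically", in a single group. There is no intravenous or other reference administration. Urine is taken for safety laboratory tests only (Section 5.2.4). Section 1.1 reports that in preclinical work "when applied topically, BZ371A did not show systemic bioavailability" and gives no figure for F in humans. Samples are taken "immediately before the application of PSI, and 15, 30, 60, 180, and 360 minutes after the application of PSI" (Section 5.3.1).

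Section 9 says "The statistical analyses will aim to describe the pharmacokinetic parameters". It gives no definition of any parameter, no estimation method and no rule for when a terminal phase counts as estimable.

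On the application area in women, the synopsis names the clitoris and both the labia majora and the labia minora. Section 6.5 opens with a general phrase covering the whole organ, then names only the clitoris and labia majora for women.

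**The concern.** CL and Vd are defined relative to the amount of drug that reaches the circulation. After a topical dose that amount is F times the applied dose, and F is not known here. Whether there is any systemic exposure is itself a study question. An analyst who follows the rule would divide the applied dose by an AUC and report the result under a name it does not have. For a fragment, the amount formed and absorbed is a further unknown, yet detection of fragments alone is enough to trigger the rule.

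A second difficulty concerns t1/2 and the volume. If absorption through skin is slower than elimination, the terminal slope measures absorption. Dividing the volume by F does not cure that, and with only two samples after 60 min the slope may be uncheckable.

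What is at stake is limited but real. Describing these parameters is the stated aim of the statistical analyses, and the trial is run "in order to guide future clinical studies". No section bases a decision on CL or Vd. Section 7.6 does use a multiple of the half-life to judge causality of adverse events, although it does not say that this trial's own estimate would be used.

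The application lists are a separate, secondary matter: the treated area behind the women's results can be read in two ways.

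**Working it through.** The plan states no figure to reproduce on this point; it asserts 12 participants without inputs.

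**Inputs from the documents.** Concentration 5 mg/mL and volume 1.5 mL (synopsis; Chart 2), so applied dose = 5 × 1.5 = 7.5 mg. Post-dose samples at 15, 30, 60, 180 and 360 min (Section 5.3.1). F is not given.

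**Step 1: what dose/AUC estimates.** AUCinf = F × Dose / CL, so Dose/AUCinf = CL/F. Likewise Dose/(λz × AUCinf) = Vz/F. Read as CL, the first overstates by 1/F:

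| Assumed F | Overstatement of CL |
|---|---|
| 10% | 1/0.1 = 10 times |
| 1% | 1/0.01 = 100 times |
| 0.1% | 1/0.001 = 1000 times |

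**Step 2: can the data separate F from CL and V?** Take a one-compartment model with first-order absorption, C(t) = F·D·ka / [V(ka − k)] × (e^(−kt) − e^(−ka·t)), with k = CL/V, D = 7.5 mg and an assumed ka of 1 per hour. Five assumed sets (F, CL in L/h, V in L) were compared: (1, 20, 30), (0.5, 10, 15), (0.1, 2, 3), (0.01, 0.2, 0.3) and (0.001, 0.02, 0.03). All give the same concentrations at 0, 15, 30, 60, 180 and 360 min: 0, 50.8, 82.5, 109.2, 64.2 and 11.9 ng/mL. CL and V can each vary 1000-fold with no change in the profile, so more participants would not help.

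**Step 3: fragments.** With fm the unknown fraction converted, Dose/AUC = CL of the fragment / (F × fm). Assumed pairs give multipliers of 0.1 × 0.5 = 0.05 or 0.01 × 0.1 = 0.001. Neither factor is known.

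**Step 4: slow absorption.** In the same model λz is the smaller of ka and k, so (Vz/F)/(V/F) = max(1, absorption t1/2 ÷ elimination t1/2).
- Assumed 0.5 h and 1 h: ratio 1.
- Assumed 3 h and 1 h: ratio 3, and the apparent t1/2 is 3 h instead of 1 h.

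Swapping ka and k in Step 2 leaves the profile identical and CL/F at 20 L/h, but moves V/F from 30 to 20 L. The data cannot tell the two cases apart.

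**Step 5: points available for the terminal slope.**

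| Observed tmax (min) | Samples after it, at most |
|---|---|
| 15 | 4 |
| 30 | 3 |
| 60 | 2 |
| 180 | 1 |
| 360 | 0 |

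A line through two points leaves no residual. A slope on post-Cmax points can be checked only if observed tmax is 30 min or earlier. These counts are maxima, because the assay limit is not given.

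**Step 6: application area.** Side by side, the synopsis includes the labia minora and the explicit list in Section 6.5 does not. The general phrase in Section 6.5 may be meant to cover them.

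**The case against.** The strongest reply is that this is a labelling slip. The main pharmacokinetic question is systemic presence, CL and Vd are contingent descriptive outputs, and any pharmacokinetic report could add the missing /F. That is fair for the parent peptide and limits the weight of the point. It does not help with fragments, and it supplies no terminal-phase rule.

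The multipliers come from assumed values of F, and the largest go with the least absorption. At F = 0.1% only 7.5 µg would be absorbed in total (7.5 mg × 0.001), which is when detection is least likely. This stands: the figures are illustrations, not an effect seen in this trial.

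Section 5.3.3 does not say in so many words that CL and Vd are to be computed for each fragment. That also stands, but the trigger is the peptide or its fragments, so if only fragments are found the rule still applies and cannot be met.

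The purpose statement in Section 3.1 goes on to name safety, tolerability and systemic bioavailability, not disposition parameters, so it supports the point less strongly than Section 9 does. A three-point rule is a convention rather than a requirement of the documents. Finally, the application-area mismatch is not an analysis matter, and the applied volume is the same in both sections; it needs reconciling but adds no weight to the main point.

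**Conclusion.** The concern holds. As written, the rule cannot be carried out: the parent peptide can yield only CL/F and Vz/F, and fragments can yield neither CL nor Vd. The first conclusion needs only a single extravascular dose with unknown F, both of which follow from the plan. The overstatement is 1/F for CL and at least 1/F for Vd; its numerical size rests on assumed F, and the threefold effect on volume and half-life rests on assumed half-lives of 3 h and 1 h. The terminal-phase limit follows from the sampling times alone.

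The consequence is confined to the case where analyte is detected. Detection, Cmax, AUC over 0–6 h and the safety objective are untouched. It should be corrected, but it does not threaten the trial. The explicit female application lists do differ; this review takes no view on which is right.

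**What to change.** Make the same change in the synopsis, Section 2.2 and Section 5.3.3, with definitions in Section 9.

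- **Parent peptide:** report Cmax, tmax and AUC(0–6 h). Replace CL and Vd with CL/F and Vz/F. Report these, t1/2 and AUCinf only where the terminal phase is estimable under a rule fixed before assay results are seen, for example at least three quantifiable samples after Cmax plus a fit criterion. Otherwise report *not estimable*.
- **Half-life:** label it apparent terminal half-life, and state that it and Vz/F may reflect absorption rather than elimination.
- **Fragments:** report Cmax, tmax, AUC(0–6 h) and, if estimable, apparent t1/2. Report no CL or Vd.
- **Application area:** reconcile the synopsis and Section 6.5 for women before dosing.

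The cost is wording in the protocol and analysis plan, with no extra samples or participants. Protocol changes need ethics committee approval under Section 8.1, and an amendment under Section 8.7.1 if they alter the study plan. The downside is that CL/F, Vz/F, t1/2 and AUCinf may be not estimable in many or all participants if tmax is 60 min or later.

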6. STUDY MEDICATION

6.1 Medication preparation

The PSI, named BZ371A, will be incorporated into a gel formulation. The formulation will be produced and stored according to good manufacturing practices (GMP), following the RDC 301 of August 21, 2019. The pharmaceutical characteristics of the API are listed in the table below:

CHART 2. IP IDENTIFICATION

| | |
|-----------------------|--|
| Active ingredient | BZ371A |
| Commercial name | Non Applicable |
| Batch | 21051801 |
| Therapeutic class | Nitric Oxide Synthase Enhancer |
| Administration method | Topical |
| Pharmaceutical form | Gel |
| Concentration | 5 mg/ml |
| Presentation | Syringes with single dose |
| Dosage regimen | 1,5 ml, single dose |
| API fabrication | CPC (Chinese Peptide Company) |
| IP production | BIOLAB Farmacêutica |
| Responsible company | Biozeus Biopharmaceutical S.A. |

The active pharmaceutical ingredient (API) was produced in accordance with good manufacturing practices (GMP) by the company CPC - Chinese Peptide Company, lot 21051801, and stored in a -20°C freezer. The API will be transported in thermal boxes containing dry ice and a digital thermometer where the maximum and minimum temperatures reached are recorded.

BIOLAB, a Brazilian pharmaceutical company, will receive the API and produce the formulation also in accordance with GMP. The finished product formulation has the following components:

CHART 3. COMPOSITION OF THE FINISHED PRODUCT

| Compounds | Quantity |
|---------------------------------|----------|
| Sodium Acetate Buffer 20mM | 60% |
| Propylene glycol | 30% |
| Pluronic F-127 | 10% |
| BZ371A Acetate (Batch 21051801) | 5 mg/ml |

The choice of BZ371A dose for this clinical study was based on physicochemical studies that determined the maximum viable concentration of the compound in this formulation. In addition, *in vivo*

studies of pharmacodynamics, biodistribution, and toxicology confirmed the efficacy and safety of this formulation, respectively.

The study drugs will be sent by the sponsor, along with all relevant documentation, in an adequate quantity for the study, including an additional quantity for sample retention and potential losses.

6.2 Packaging and labelling

The product will be available in 3ml syringes containing 1.5ml of the formulation, for single-dose administration. All syringes will be provided in individual laminated bags, of the stand-up pouch type weighing 250 grams, with the label containing the necessary information for clinical research according to the regulations in force in the country.

The label model to be used will contain all the labeling information required by ANVISA for products intended for clinical research, as shown in Figure 1 below:

| | |
|---|--|
| Sponsor: | |
| Study Protocol | |
| Responsible investigator (name, Regional Council identification number): | |
| Responsible pharmacist (name, Regional Council identification number): | |
| Pharmaceutical form: | |
| Batch: | |
| Fabrication date (month/year): | |
| Expiration date (month/year): | |
| Weight: | |
| Storage conditions: | |
| How to use it: | |
| Administration Route: | |
| ⚠ ATENTION! | |
| Product exclusively destined for the Clinical Research. | |
| This product should not be commercialized. | |
| Should be kept out of children's reach. | |
| This product should not be used in other people. Exclusive use for whom is destined to. | |
| This packaging should not be discarded and should be given back in the next visit, together with the product, even though it have not been entirely used. | |
| This product should be used as medical orientation. | |
| In case of any doubts, please contact the Clinical Research facility and ask for Investigators Name and telephone | |

FIGURE 1. LABEL MODEL FOR PRODUCTS INTENDED FOR CLINICAL RESEARCH (ANVISA)

6.3 Medication storage

The IP must be stored in a secure location equipped with locked cabinets and restricted access, protected from light and moisture, and at room temperature between 20 to 25°C. Only authorized personnel will have access to the products, and a document controlling access to the storage area must be available for inspection during possible monitoring and/or audits.

Deviation from storage requirements, including any actions taken, must be documented and immediately reported to the Sponsor. Once the deviation is identified, the IP should be placed in quarantine, and it should not be used until the Sponsor provides specific documentation permitting its use.

All drug packaging (used or unused) should be stored at the Research Center, so that at the end of the study, they can be sent for final disposal, which is the responsibility of the Sponsor.

